### **1.1 Primary Objectives**

- 1.1.1 To determine the rate of local regional control (LRC) at 5 years in patients with early and intermediate stage HPV related oropharynx cancer treated with surgery alone.
- 1.1.2 To determine the rate of progression free survival (PFS) at 5 years in patients with early and intermediate stage HPV related oropharynx cancer treated with surgery alone.
- 1.1.3 To determine overall survival (OS) at 5 years in patients with early and intermediate stage HPV related oropharynx cancer treated with surgery alone.
- 1.1.4 To determine the rate of local regional control (LRC) at 3 years in patients with HPV related oropharynx cancer treated with a de-intensified adjuvant protocol.
- 1.1.5 To determine the rate of progression free survival (PFS) at 3 years in patients with HPV related oropharynx cancer treated with a de-intensified adjuvant protocol.
- 1.1.6 To determine overall survival (OS) at 3 years in patients with HPV related oropharynx cancer treated with a de-intensified adjuvant protocol.
- 1.1.7 To determine the rate of PFS (Ultimate Disease Control – UDC) and of OAS after secondary therapy for patients treated with surgery only who have local regional relapse at 5 years
- 1.1.8 To determine the rate of PFS (UDC) and OAS after secondary therapy for patients who relapse with distant disease after surgery only
- 1.1.9 To quantify the quality of life of patients treated with this protocol at 3 years

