## 11.0 MEASUREMENT OF EFFECT

### 11.1.1 Definitions

Evaluable for toxicity. All participants who go on to surgery will be evaluable for toxicity from the time of their first treatment. Patients who are screened will be evaluated and the reason for screen failure will be recorded

Evaluable for Primary Outcome: Only patients who are entered and have surgery will be eligible for assessment of the primary outcomes (LRC, PFS). All patients who have had surgery will be analyzed on an ITT for LRC, PFS, and survival.

Progression-Free Survival: Progression-Free Survival (PFS) is defined as the duration of time from start of treatment to time of objective disease progression or death.

Local Regional Control (LRC) will be defined as local and regional control of disease, censored for death.

Overall Survival (OAS) will be defined as alive at the time of analysis, this will be analyzed as for the entire trial, for all randomized patients and only for those patients randomized who received one dose of radiotherapy.

Post Recurrence LRC: Surveillance Patients who recur will be assessed for LRC post treatment for their initial recurrence

Post Recurrence PFS Surveillance Patients who recur will be assessed for PFS post treatment for their initial recurrence

Ultimate Disease Control will be defined as those patients who are alive and disease free at the time of analysis

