## 16.0 STATISTICAL CONSIDERATIONS

### 16.1 Study Design/Endpoints

This is a prospective clinical trial evaluating surgery alone for early stage HPV related oropharyngeal squamous cell carcinoma. The primary endpoints are the rate of local-regional control OAS, and PFS at 3 years in patients with HPV 16 and p16+ related head and neck cancer, treated with surgery alone. The secondary objectives include 5 year PFS, LRC, Overall Survival, Ultimate Disease Control, QOL, site of failure and rate of salvage, as well as establishing biomarkers predictive of treatment outcomes and collection of tumor tissue, germline DNA and a plasma bank for future studies. The main study hypotheses is that OAS and UDC at 5 years for surgery alone for early stage HPV related oropharyngeal squamous cell carcinoma is equivalent to current regimens involving standardized post-operative radiotherapy (>85%) and that LRC without radiotherapy will be > 50%. Additional Hypotheses relate to Group 2 and 3 - OAS and PFS at 5 years for reduced dose XRT and CRT intermediate stage HPV related oropharyngeal squamous cell carcinoma is equivalent to current regimens involving standardized post-operative radiotherapy (>85%) and that LRC will be > 85%.

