### 16.2 Sample Size/Accrual Rate

Sample size justification:

The proposed sample size of 100 for Group 1 has been determined to ensure that an upper bound for recurrence may be estimated with adequate precision, defined as within 8-12% of the true recurrence rate. The upper bound is estimated by the posterior probability of recurrence given the observed data, assuming a non-informative beta(1,1) prior distribution. The table below provides the upper 95% bound (from the Bayesian credible interval) assuming the true rate of recurrence is .1,.2,.3,.4, or .5 and 100 patients are studied.

True recurrence	Upper 95% bound
.1	.184
.2	.301
.3	.413
.4	.516

CONFIDENTIAL

This document is confidential. Do not disclose or use except as authorized.

[figure not shown]

.5

.614

The various specific aims outlined in Aim 1 share a common objective: determining rates of important measures of treatment response (progression-free survival, overall survival, local regional control and ultimate disease control) for patients treated with surgery alone and compare them to those expected in patients with similar diagnostic criteria. We will assess this overall objective by using a Bayesian approach to estimate the posterior probability distributions for each respective sub-aim based on observed outcomes. This approach permits estimating probabilities with which a specified rate of interest exceeds a threshold value (e.g.; 50% local regional control, 85% overall survival, etc.)

Our approach begins with the premise that surgery alone offers no improvement in expected outcomes. This is an exact correspondence to a "null hypothesis". We incorporate this assumption through a prior distribution for each suspected rate; for example, for Group I patients we would assume that the rate of local regional control (LRC) at three years is 50%. After the studies are conducted, each respective rate is combined with the "null" prior distribution through Bayes' Theorem to yield the posterior distribution for the rate. The table below depicts simulated results for the posterior LRC ( $\theta$ ) using 100 patients based on two differing assumptions: that LRC at three years is 50% ( $p=0.5$  shown on the left) and 85% ( $p=0.85$  shown on the right).

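### Ultimate Disease Control is defined as status on the day of analysis while the main hypothesis needs it at 5 years, with no rule for shorter follow-up, and the objectives reuse its name for a different quantity

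*Combined protocol and SAP*

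**What the plan says.** Section 16.1 sets the claim: "The main study hypotheses is that OAS and UDC at 5 years for surgery alone" is "equivalent to current regimens involving standardized post-operative radiotherapy (>85%) and that LRC without radiotherapy will be > 50"%. The same section also lists UDC among the 5-year secondary objectives.

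Section 11.1.1 defines the two measures without a time point: "Ultimate Disease Control will be defined as those patients who are alive and disease free at the time of analysis", and "Overall Survival (OAS) will be defined as alive at the time of analysis". Neither definition gives a time origin or a rule for incomplete follow-up, and the UDC definition gives no denominator.

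Section 16.2 names the rates to be estimated by Bayesian posteriors as "progression-free survival, overall survival, local regional control and ultimate disease control", so PFS and UDC are separate there. Sections 16.4 and 16.5 plan Kaplan-Meier or log-rank analyses for DFS, LRC and overall survival. UDC does not appear in either.

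In Section 1.1, objective 1.1.7 concerns "the rate of PFS (Ultimate Disease Control – UDC) and of OAS after secondary therapy" in surgery-only patients with locoregional relapse. Objective 1.1.8 reads: "To determine the rate of PFS (UDC) and OAS after secondary therapy for patients who relapse with distant disease after surgery only".

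On data collection, Section 6.1 plans follow-up for 5 years after study treatment, and the Group I schedule in Section 5.0 has imaging to 60 months. Section 6.2 lists progression or relapse as a reason for removal from study. Section 1.0 says that patients taken off study are followed for survival.

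**The concern.** The case for surgery alone rests on the argument that patients who relapse can be treated successfully afterwards. UDC is the measure that tests this for disease control. The trial has one surgery-alone group and a fixed 85% threshold, so no concurrent control would reveal a rate that was too high because of short follow-up.

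Patients enter over time. Under the wording of Section 11.1.1, a patient operated on a few months before the data cut and still well counts as a success, exactly like a patient who is well at 5 years. If that count goes into the Section 16.2 posterior, the answer depends partly on when the database is cut.

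Two further problems affect what the number means. The name UDC covers relapsed patients only in the objectives, but surgery-alone patients generally in Section 16.1. And the patients whose outcome separates UDC from PFS, those who relapse and are salvaged, are the ones for whom later disease status may not be recorded.

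**Working it through.** The plan gives no UDC figure to reproduce; 85% is a threshold. The check compares the passages and then illustrates the size.

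**1. Time anchor.** Section 16.1 needs the rate at 5 years. Section 11.1.1 counts status at analysis. Section 16.2 gives a posterior for a rate with no censoring rule, and Sections 16.4 and 16.5 do not mention UDC. No passage says how a patient with, for example, 18 months of follow-up is to be handled.

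**2. Size of the date effect.**
- Assumptions: follow-up spread evenly from a to b years; a constant hazard λ of leaving the alive-and-disease-free state; no return to it. None of these is in the documents.
- Formula: crude proportion = [exp(−λa) − exp(−λb)] / [λ(b − a)], with λ = −ln(5-year rate)/5.
- True 5-year rate 80%: λ = 0.2231/5 = 0.0446.
  - 0 to 5 years: (1 − 0.80)/0.2231 = 89.6%.
  - 1 to 5 years: (0.9564 − 0.80)/(0.0446 × 4) = 87.6%.
- True 5-year rate 85%: λ = 0.1625/5 = 0.0325.
  - 0 to 5 years: (1 − 0.85)/0.1625 = 92.3%.

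**3. Effect on the posterior.** With the Group I sample size of 100 and the beta(1,1) prior from Section 16.2, x successes give a Beta(1 + x, 101 − x) posterior.

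| Successes out of 100 | P(rate > 0.85) |
|---|---|
| 80 | 0.07 |
| 88 | 0.77 |
| 90 | 0.91 |

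A treatment whose true 5-year rate misses the threshold at 80% would look likely to exceed it if about 90 of 100 patients were counted as successes at an early cut.

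**4. What UDC has to count.** Take LRC at the 50% floor of the Section 16.1 hypothesis. A UDC of 85% then needs at least (0.85 − 0.50)/0.50 = 70% of the locoregional failures to be salvaged and counted as successes, even with no other failures. This agrees with the literal Section 11.1.1 wording, under which a salvaged patient who is disease free is a success.

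**5. The label.** Section 11.1.1 defines PFS from the start of treatment: "Progression-Free Survival (PFS) is defined as the duration of time from start of treatment to time of objective disease progression or death". It separately defines Post Recurrence PFS, assessed after treatment of the initial recurrence in surveillance patients. Objectives 1.1.7 and 1.1.8 describe that second quantity but call it UDC. The denominator there is relapsed patients; in Section 16.1 it is surgery-alone patients.

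**6. Measurability.** Sections 6.2 and 1.0 together allow a relapsed patient to be removed and then followed for survival only. Disease status at 60 months after salvage is therefore not assured.

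**The case against.** **The 5-year horizon is stated.** Section 16.1 names it, Section 6.1 plans the follow-up, Group I imaging runs to 60 months, and the LRC example in Section 16.2 is anchored at three years. Read together, these passages show that a 5-year rate is intended, and it is an inference that a crude early count would be used. This stands as to intent. It does not supply a rule for patients with less than 5 years of follow-up, and the only written definition ignores the horizon.

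**The objectives do not contradict Section 11.1.1 on salvage.** Because they pair PFS with UDC, a reader might infer that a salvaged relapse is a success in Section 11.1.1 and a failure in the objectives. The documents do not support that. Both objectives specify the period after secondary therapy in patients who have already relapsed, so the first relapse is the entry condition and not the failure event. What remains is a wrong label and a different denominator.

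**The percentages are fragile.** Every follow-up window is assumed. The model is also one-way, whereas salvage returns patients to the disease-free state. Windows beyond 5 years would exceed the follow-up in Section 6.1 and are not relied on here. This stands: the figures show a possible size, not a forecast. An early cut inflates the count only if the disease-free share falls with time. Without that, dependence on the date remains but its direction is uncertain, since a patient in the middle of salvage treatment at the cut counts as a failure.

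**UDC carries limited weight.** Section 16.1 also lists it as secondary, Section 11.1.1 names LRC and PFS as the primary outcomes, and no stopping or decision rule uses UDC. It is nevertheless one of the two measures in the 5-year statement of the main hypothesis.

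**Conclusion.** The point holds as a defect of definition. The rule in Section 11.1.1 does not estimate the 5-year quantity in Section 16.1, and nothing in Sections 16.2, 16.4 or 16.5 corrects it. With staggered entry, the reported rate depends on the cut date.

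Under the stated assumptions, the overstatement for a true rate of 80% is about 10 percentage points with follow-up over 0 to 5 years (89.6 − 80) and about 8 points over 1 to 5 years (87.6 − 80). Either would carry the estimate past 85%. The exact size cannot be known from the documents.

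The overall survival definition has the same wording but a smaller problem, because Section 16.5 already plans Kaplan-Meier curves. The use of UDC in objectives 1.1.7 and 1.1.8 is a mislabel with a conflicting denominator; it does not reverse how salvaged patients are counted. The follow-up passages leave open whether UDC can be measured in the patients who matter most for it.

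**What to change.** 1. In Section 11.1.1, define UDC as alive and disease free 60 months after surgery, with all Group I patients as the denominator. State that patients who relapsed but are salvaged and disease free at 60 months are successes. Estimate the rate once every Group I patient has 60 months of potential follow-up. Otherwise use a censoring-aware estimate of being in the disease-free state at 60 months, such as a multistate estimate. A Kaplan-Meier curve of time to first failure would not do, because patients can return to that state.
2. Define overall survival as time from surgery to death, read at 60 months with the Kaplan-Meier method already in Section 16.5.
3. In objectives 1.1.7 and 1.1.8, remove UDC as a label for PFS and use the existing Section 11.1.1 term, Post Recurrence PFS.
4. Reconcile Sections 6.2 and 1.0 with these endpoints, so that disease status as well as survival is recorded to 60 months for relapsed Group I patients.

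The cost is wording in Sections 1.0, 1.1, 6.2 and 11.1.1, an analysis sentence for UDC in Section 16, and one more follow-up data item after relapse. No additional patients are needed. The UDC figure will come later and may be less favourable, and a crude count from an early cut can no longer be presented as the 5-year result.

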## 12.0 ASSESSMENT OF QUALITY OF LIFE AND PATIENT REPORTED SYMPTOMS

Head and neck cancer often arises in cosmetically or functionally important areas. Thus, the ability to eat, speak, breathe easily, as well as the patient's overall sense of comfort is frequently affected by therapy. In addition to these disease-specific symptoms, patients with head and neck cancer may also experience symptoms related to surgery (e.g. disfigurement) or to radiation therapy (e.g., dysphagia, xerostomia, and mucositis). These may lead to feeling of general overall sickness and can potentially result in social isolation. Patient-reported symptoms tend to be more severe than those recorded by physicians, patient reported outcome instruments are increasingly being used to measure symptom burden, functionality and quality of life. It can provide more comprehensive and improved toxicity data. Quality of life (QOL) assessment is a multi-dimensional construct that involves an individual's subjective assessment of the impact of an illness or treatment on his/her physical, psychological, social, and somatic functioning and general well-being. The European Organization for Research and Treatment of Cancer Core measure (EORTC QLQ-C30) is a well validated cancer-specific QOL scale that is used as a generic measurement for patients with cancer that in head and neck patients is used in conjunction with the site specific measurement tool EORTC QLQ H&N35. The M.D. Anderson Symptom Inventory-Head and Neck (MDASI-HN) module is a validated instrument that provides a brief measure of the symptom distress experienced by the head and neck cancer patients as a result of their disease and/or treatment. This symptom burden instrument was closely associated with the severity of radiation-induced mucositis. The MDA Xerostomia and Dysphagia questionnaires are radiotherapy/head and neck cancer directed questions which have a robust, validated assessment the specific concerns of swallowing and salivary function in head and neck cancer treated patients.

CONFIDENTIAL

This document is confidential. Do not disclose or use except as authorized.

In this study, patients will complete the EORTC QLQ-C30, EORTC QLQ H&N35, MDASI-HN, the MDADI-HN (dysphagia) and xerostomia questionnaires prior to therapy and then at 3, 6, 12 and every 12 months after therapy for 5 years for all patients. During the concomitant chemo-radiation phase of treatment, in order to avoid patient fatigue, the EORTC QLQ-C30, EORTC QLQ H&N35, MDASI-HN module, MDADI-HN (dysphagia) and xerostomia questionnaires will be completed on pre and weeks 5, 7 and post rx 3 months; and the . The adverse events assessments, the (see table). As shown in the statistical plan we will use these assessments in conjunction with adverse events assessments to compare the experiment and control arms of this study.

	Pre-Study	CRT	Post-Study Follow-up
Informed Consent	To be obtained before enrollment		
EORTC QLQ-C30, EORTC QLQ H&N35	Within 10 days before registration	pre and weeks 5 7 and post rx 3 months	3, 6, 12, and every 12 months for 5 years
MDASI-HN	Within 10 days before registration	pre and weeks 5 7 and post rx 3 months	3, 6, 12, and every 12 months for 5 years
MDADI-HN (Dysphagia Assessment Questionnaire)	Within 10 days before registration	pre and weeks 5 7 and post rx 3 months	3, 6, 12, and every 12 months for 5 years
Xerostomia		pre and weeks 5 7 and post rx 3 months	3, 6, 12, and every 12 months for 5 years

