## **4.0 REGISTRATION PROCEDURES**

After the patient signs the informed consent the patient will be registered for screening and once the investigator has verified that the patient meets all inclusion/exclusion criteria, the patient will be registered for and started on the protocol. Patients who lack p16 and HPV PCR may proceed to surgery however they will not be assigned to an experimental group and registered on the protocol until p16 IHC and HPV PCR are completed and positive. The verification of patient's eligibility and screening completion will be performed centrally after the receipt of the patient primary post-surgical registration form. It is mandatory not to exceed 21 days between the date of registration for screening and the start of the study treatment (surgery). In any case, all events occurring after the registration for therapy must be recorded in the case report form and will be taken into account in the analysis, whether the patient received the study treatment or not. Patient must receive surgery and be p16 IHC and HPV PCR positive to be included in the intent to treat analysis. Patients found to not meet entry criteria will be offered best therapy.

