#### Group I Protocol

- No adjuvant therapy
- Clinical evaluations every 3-4 months the first year

PET or CT at 4 months, 12 months, 24 months, 36 months 48 54, and 60 months unless clinically indicated

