#### Group II Protocol

- Postoperative XRT 5000 cGy

CONFIDENTIAL

This document is confidential. Do not disclose or use except as authorized.

- Clinical evaluations every 3-4months during the first year
- PET or CT at 4 months, , 12 months, 24 months. 36 months 48 54, 60 unless clinically indicated. (Newer data suggests we can substitute quarterly cfDNA after initial clear PET through year 2 and then q 6 months through year 4 and then yearly through year 6. Physicians have the option to follow with cfDNA in all groups, but with imaging, as indicated).

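### The Section 12 table gives the xerostomia questionnaire no pre-study assessment, although the text above it requires one before therapy for all patients

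*Combined protocol and SAP*

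**What the plan says.** Section 12.0 names five instruments: EORTC QLQ-C30, EORTC QLQ-H&N35, MDASI-HN, the MD Anderson dysphagia inventory and the xerostomia questionnaire. For the last of these the sentence ends "xerostomia questionnaires prior to therapy and then at 3, 6, 12 and every 12 months after therapy for 5 years for all patients". A second sentence sets the schedule for the chemoradiation phase. It opens "During the concomitant chemo-radiation phase of treatment, in order to avoid patient fatigue" and places the same five instruments at "pre and weeks 5, 7 and post rx 3 months".

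The table that follows has three columns: Pre-Study, CRT and Post-Study Follow-up. Under Pre-Study, the EORTC row (both instruments), the MDASI-HN row and the dysphagia row each read "Within 10 days before registration". The Xerostomia row is empty there. Its first entry is in the CRT column, and its follow-up entry matches the other rows.

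Quality of life enters the objectives at 1.1.9, which reads "To quantify the quality of life of patients treated with this protocol at 3 years" and is listed as primary. Objective 1.2.6 repeats it at 5 years as secondary.

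**The concern.** The trial tests whether radiotherapy can be omitted or reduced after surgery. Section 12.0 lists xerostomia among the symptoms of radiation and describes the xerostomia and dysphagia questionnaires as validated measures of salivary function and swallowing. The XQ is therefore the instrument aimed most directly at one of the harms that the trial hopes to spare patients.

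A score from before surgery separates dry mouth that the patient already had from dry mouth that followed treatment. That matters more here than in a randomised trial, because pathology assigns the groups and nothing balances their starting values. Section 12.0 also says that the assessments will be used to compare arms. A baseline missed before surgery cannot be collected afterwards.

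**Working it through.** No figure in the plan needs reproducing. The check compares the schedule texts with one another.

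**1. When therapy starts.** Section 4.0 requires no more than 21 days between registration for screening and "the start of the study treatment (surgery". Study treatment thus begins with surgery. The Group I protocol in Section 5.0 reads "No adjuvant therapy", so for Group I an assessment before therapy can only be one before surgery. The requirement covers all patients, so it cannot be met by reading therapy as radiotherapy.

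**2. The Pre-Study column.** Of four questionnaire rows, three are filled, covering four of the five instruments. Xerostomia is the only questionnaire row left blank.

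**3. First XQ by group under each reading.**

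| Group | Treatment after surgery | First XQ, text followed | First XQ, table followed |
|---|---|---|---|
| I | None | Before surgery | 3 months after surgery |
| II | Radiotherapy alone | Before surgery | Unclear: before radiotherapy if the CRT column covers it, otherwise at a later assessment |
| IIIA, IIIB | Chemoradiotherapy | Before surgery | Before chemoradiotherapy, after surgery |

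Group II is unclear because its protocol reads "Postoperative XRT 5000 cGy", with no chemotherapy, while the column is headed CRT and the text speaks of concomitant chemoradiation. The Section 10.0 calendar, however, has a treatment column that names groups 2 and 3 together. Either way, a pre-surgical XQ exists in four of four groups under the text and in none of four under the table.

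**4. Effect on a change score.** Let X0 be the score before surgery, X1 the score after surgery and before chemoradiotherapy, and X36 the score at 36 months.

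- Change from the pre-surgical state is X36 − X0.
- Group I under the table: X0 and X1 do not exist, so no change from before treatment can be formed.
- Groups IIIA and IIIB under the table: only X36 − X1 is available. It equals (X36 − X0) − (X1 − X0), so it leaves out whatever surgery did to the score.

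The observed score X36 is scheduled in every group under both readings.

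**5. Whether another schedule fills the gap.** The Section 10.0 calendar has no xerostomia row. The correlative studies calendar refers the reader to Section 16.0 for quality of life, but Section 16.0 contains no assessment schedule. Only the one sentence in Section 12.0 supplies the pre-therapy XQ.

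**6. Other baseline dry-mouth data.** Two instruments with a filled Pre-Study cell ask about dry mouth (Appendix 3): H&N35 item 41, on a four-point scale over the past week, and MDASI-HN item 10, scored 0 to 10 over the last 24 hours. H&N35 item 42 asks about sticky saliva. The XQ has eight items, each scored 0 to 10 over the past week.

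**The case against.** The strongest reply is that the stated design already includes the baseline. The sentence is explicit and sits directly above the table, and nothing in the documents shows that any assessment was missed. That stands: the fault is a contradiction between text and table, and the loss occurs only where the table is followed.

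The blank cell might also be an artefact of reading the PDF. This cannot be excluded, but the row's other entries sit in the right columns and the neighbouring rows are intact, so it is unlikely. The Section 10.0 calendar adds little support, since it also omits the EORTC instruments and the MDASI-HN. It shows only that no other schedule corrects the table.

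Three stronger readings are tempting, and the documents do not support them.

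- A reader might infer that Group I has no dry-mouth baseline of any kind. H&N35 item 41 and MDASI-HN item 10 are scheduled pre-study for every group. What would be missing is the XQ baseline.
- A reader might infer that Groups II and III both have a post-surgical baseline. For Group II that depends on how the CRT column is read.
- A reader might infer that a primary analysis fails. Objective 1.1.9 names neither the XQ nor change from baseline, Sections 16.4 and 16.5 specify no quality-of-life analysis, and the 3-year XQ is scheduled under either reading.

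**Conclusion.** The contradiction is real and should be resolved. If sites follow the table, none of the four groups has a pre-surgical XQ. That includes the planned 100 patients in Group I, who would have no XQ until 3 months. Change from the pre-surgical state could not be calculated, and the dry-mouth data from before surgery would be items in the H&N35 and MDASI-HN, which do not replace an eight-item scale.

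This rests on two assumptions: that the blank cell is in the protocol itself, and that at least some sites schedule from the table. How many do is unknown, so the number of baselines actually lost cannot be stated. The effect is on the interpretation of XQ scores. It does not remove the 3-year scores themselves or any analysis that the plan specifies.

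**What to change.** In the Section 12.0 table, enter in the Xerostomia row the window that the other rows carry, "Within 10 days before registration", and state that it falls before surgery for all groups. The addition is needed because Section 4.1 describes registration at several points, the last of them after surgery. Keep the CRT assessment as an additional time point, and state whether that column applies to Group II. Correct the correlative calendar so that it refers to Section 12.0 for quality of life.

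For any patient already enrolled without a pre-surgical XQ, report the observed scores and state that no XQ baseline exists.

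The cost is one table cell, two clarifications of wording, and eight items at a visit where four other instruments are already given. The change carries out what the text already requires and leaves treatment untouched.
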